Visit 3 (Laboratory Session I) – Day 5 Participants will provide a urine sample (drug toxicology), and a one vial blood sample (β -endorphin, hormone levels). Participants will then complete a series of assessments (**Table 1**) and receive a single oral dose of yohimbine or yohimbine-matched placebo. Fifteen minutes later, participants will administer a dose of oxytocin or oxytocin-matched placebo (40 IU, 4 sprays per nostril), after 30 min the first sample of saliva (cortisol and oxytocin) will be collected and the cue-reactivity will begin (112). Cue-Reactivity (CR) Task will be administered in a similar manner to other published studies (72, 73) for individuals with OUD with cues selected based on patients' drug experience. To measure cue-induced opioid craving, participants will a view images of neutral stimuli and then of opioid drug use (24). Participants will rate their craving via drug visual analog scale (VAS) and the second sample of saliva cortisol will be collected (45 min later). Vital signs will be monitored during the entire procedure. Participants will then complete Post-Cue measures, will have their vital signs measured and conduct the last sample of saliva.

Visit 4 (Laboratory Session II) – Day 7 Participants will come back after two days. The procedure will be similar to Visit 3 but they will receive the opposite condition (yohimbine or yohimbine-matched placebo).

A two-day washout period will occur followed by initiation of the opposite intranasal medication condition (i.e. oxytocin and oxytocin-matched placebo) to be administered for one week starting at day 9.

Visit 5 (Laboratory Session III) – Day 14 Participants will complete the lab procedures as described in Visit 3 and 4, however, this time will be administered the opposite oxytocin condition (i.e. oxytocin or oxytocin-matched placebo). Participants will also receive yohimbine or yohimbine-matched placebo (counterbalanced).

Visit 6 (Laboratory Session IV) – Day 17 Participants will come back after two days. The procedures will be completed as described in Visits 3-5, but they will receive the opposite condition (yohimbine or yohimbine-matched placebo).

Visit 7 (follow-up) – Day 20 After three days, participants will come to the lab for the final assessments (Table 1).

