For those that have previously completed the study and will be re-enrolled in the opposite medication conditions, they will go through an additional two visits for safety criteria and to once again confirm eligibility: visit A and Visit B

Visit A: Participants will review their brief medical history questionnaire with the nurse practitioner, and compete assessments about any anxious or depressive symptoms.

Visit B: Upon completion of visits 5 and 6 where participants were randomized to the opposite medication condition, they will once again come to the lab to complete the final assessments **(Table 1)**.

Medication compliance: To ensure study medication compliance, oxytocin levels will be measured at screening (to determine oxytocin baseline values), at Visit 3, 4, 5 and 6. Buprenorphine levels will be checked by urine at each visit, in order to ensure ORT compliance and reduce the risk of withdrawal after study conclusion.

Assessments Demographic and baseline characteristics will be assessed according the CADRE standardized format (**Attachment B**). Additionally, specific for this project, we will include (**Attachment G**):

Opioid craving/withdrawal. a) Clinical Opiate Withdrawal Scale (COWS) (113) an 11-item scale that measures the stage or severity of opiate withdrawal and the level of physical dependence, b) Opioid Craving Scale (OCS) a 3-item scale adapted from the 3-item Cocaine Craving Scale (114), that assesses opioid craving and c) Opioid Timeline Follow-back (115) a calendar-assisted interview that will help participants estimate their amount of opioid use over the last 90 days.

Mood, Anxiety and Trauma Measures, in addition to the CADRE standardized assessments, we included anxiety and stress measure: a) Hamilton Anxiety Rating Scale (HAM-A) (116) is a 14-item scale that measures anxiety symptoms (psychic anxiety and somatic anxiety), b) Hamilton Rating Scale for Depression HAM-D a 21-item scale designed to assess potential depressive symptoms, and c) State-Trait Anxiety Inventory (STAI) (117) is 40-item measure that is split into state anxiety (20 items) and trait anxiety (20 items).

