The list of the CADRE standardized assessments and measures is attached (**Attachment B**) and *ad hoc* assessments administer during the study period is described in **Table 1** (**Attachment G**). Other potential effects of oxytocin as pharmacotherapy for OUD on relapse, drug-taking or subjective rating of drug effect will be monitored throughout the study.

TABLE 1 – Assessments						
Measure	Visit 1 Screening	Visit 2 Randomization	Visit 3, 4, 5 and 6 Laboratory	Visit 7 Follow-up	Visit A	Visit B
Adverse Events Evaluation (AEE)		x	x	x		X
Clinical Opiate Withdrawal Scale (COWS)	x	x	x	x	X	X
Concomitant medications, nicotine and marihuana use	x	x	x	x	X	x
Prior and Concomitant Medications Log	X	x	x	X	X	X
Hamilton anxiety rating scale (HAM-A)	x	x	х	x	X	X
Hormone blood collection (blood and saliva)	x		х			
Opioid Craving Scale (OCS)	x	x	x	x		X
State Anxiety Inventory-State (STAI-State)	x		х		X	
Trait Anxiety Inventory-Trait (STAI-Trait)	x					
Study medication accountability			x			
Buprenorphine urine level	x	x	x	x	X	X
Menopausal Health Questionnaire	x					
Hamilton Rating Scale for Depression HAMD	x				X	
PTSD PCL 5		x				
Drug Attention Scale (DAS)			x			

Desire for Drug Questionnaire (DDQ)		x	
Obsessive Compulsive Drug Use Scale (OCDUS)		x	
Drug or Treatment Drug Craving Questionnaire		x	

Clinical Laboratory Core (CLC)

Measures Aim 3 of the CADRE's Clinical Laboratory Core (CLC) is to build a center-wide database of transdiagnostic biological and environmental factors associated with the development and progression of SUDs and chronic disease. This database will enable CADRE project and pilot investigators to test multi-causal models of the relationships between SUDs and chronic disease. Measures to be included in all projects in service of this aim include: the MINI 7.0.2. (brief patient-completed structured clinical interview for DSM-5 disorders), measures of stigma, trauma, family history of alcohol/substance use, affective dysregulation (anhedonia), behavioral dysregulation (impulsivity), sleep, physical activity, health-related quality of life, and blood samples from which DNA will be extracted and biobanked for future analysis. All measures are described in the CLC Research Plan. The CLC measures will be included in each project's baseline assessment battery, along with project-specific measures, by the CLC's data management team to ensure uniformity in item wording and response format across projects.

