- 5. To protect against or minimize any risk of side effects associated with oxytocin, yohimbine or any drug-drug interactions, potential risks will be judiciously outlined to participants and thorough screening procedures will be in place to minimize recruitment of those that might be at a higher risk of adverse events. The study physician ([name]) and the CADRE NP will carefully review all participant screens and the PI will evaluate the individual medication profile to minimize any risk association with the medication. The participants will be instructed on the proper administration of the medication and they will return the spray bottle at the last visit. The safety of oxytocin is supported by other work with intranasal oxytocin spray (102, 103). No adverse events or side-effects were reported during the studies. [name] contact information will be provided to participants so that participants can contact him between visits if necessary.
- 6. To protect against or minimize any discomfort from opioid withdrawal, participants will be closely monitored throughout the study. Opioid withdrawal will be assessed before each visit and since individuals with a COW > 0 will be excluded from the study at screening, we don't expect withdrawal from opioids to be severe. [name] and/or the CADRE NP will be accessible 24/7 during the study and participants will be instructed to call if they experience any withdrawal symptoms. Emergency medical services will be immediately called if a serious adverse event arises during the study. Opioid withdrawal symptoms can be uncomfortable but are not dangerous.
- 7. To protect against or minimize any discomfort from opioid craving during cue reactivity, participants will be closely monitored throughout the laboratory session. Buprenorphine/naloxone or methadone level will be assessed at visit 3 to ensure ORT compliance. Participants' vital signs (BP, HR and MAP) and opioid craving with behavioral assessments will be monitored during the entire session.
- 8. The safety of yohimbine (32.4mg), formulated by Bayview Pharmacy is administered below the therapeutic index to a dose considered unsafe (>100mg). Furthermore, yohimbine will be administered only once, during the laboratory session.

The protocol involves an intervention proposed as an adjunct therapy to the standard care. There are minimal risk for participants in their daily lives, however they may feel discomfort during the

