laboratory procedures (stress-induction). See below additional consideration to prevent the additional risks:

- JB Pharmacy will provide the oxytocin (40 IU intranasal) and yohimbine (32.4 mg, oral) that will be administered at CAAS under team supervision prior to the laboratory session. Risks of medications will be minimized through careful and detailed screening of participants by the PI, ([name]) who is a trained pharmacist and pharmacologist and the co-I, and study physician ([name]) who is a practicing physician and addiction psychiatrist, to minimize recruitment of those who might be at higher risk for adverse events, as well as careful and detailed monitoring of adverse events and participant well-being during the study.
- Oxytocin. There are usually no side effects in individuals that administer intranasal oxytocin spray at the dose provided in this proposed project. The half-life of intranasal oxytocin in serum is 3-17 minutes and therefore side effects should be minimal. Common side effects include: relaxation, irritability and stomach cramps. Less common side effects that are reported at higher doses include: mild dizziness, dry mouth, nausea, vomiting, nasal irritation, runny nose, or tearing of the eyes are common with medication given by nasal spray. Participants will be instructed on how to properly administer the nasal spray by the CADRE NP, with an empty sprayer bottle. The participant will administer the first dose while at the CADRE laboratory to ensure correct administration. Participants will be instructed to stop taking the medication and to call the PI if any side effects or adverse events as a result of the medication occur. The PI will then contact [name] and/or the CADRE NP who will recommend next steps. Participants may withdraw from the study at any time if they do not feel comfortable administering the medication and will be compensated for sessions that they have completed. To protect against or minimize any risk associated with opioid craving after the opioid cue-reactivity task, participants' vital signs and opioid craving with behavioral assessments will be monitored. If a clinically significant increase in craving were to occur, participants may require clinical management. [name] and/or the CADRE NP will be immediately called and will evaluate each participant on a case-by-case scenario.

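### Oxytocin levels at laboratory visits, the stated compliance measure for the study spray, say essentially nothing about home dosing over the preceding days

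*Protocol*

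**What the plan says.** The Medication compliance paragraph (Protocol Part III, section 3) gives one measure for the study spray: "To ensure study medication compliance, oxytocin levels will be measured at screening (to determine oxytocin baseline values), at Visit 3, 4, 5 and 6". It names neither the sample type nor the time relative to dosing.

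The Visit 3 description in the same section supplies the timing, and Visits 4-6 follow the same procedure. After yohimbine or its placebo, "Fifteen minutes later, participants will administer a dose of oxytocin or oxytocin-matched placebo"; then "after 30 min the first sample of saliva (cortisol and oxytocin) will be collected". Section 7 says that the oxytocin and yohimbine are drugs "that will be administered at CAAS under team supervision prior to the laboratory session". Its oxytocin paragraph adds: "The half-life of intranasal oxytocin in serum is 3-17 minutes and therefore side effects should be minimal".

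Two other adherence items appear. The assessment table in section 3 has a row, "Study medication accountability", ticked for Visits 3-6 with no method or threshold. Section 7 says of participants that "they will return the spray bottle at the last visit".

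The SAP (Statistical analysis, Outcomes) compares seven days of oxytocin with matched placebo. Its intention-to-treat set requires only one dose of spray, and it contains no adherence analysis.

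**The concern.** A compliance measure should differ between someone who used the spray at home and someone who did not. Here the sample comes shortly after a dose taken in the laboratory, and the drug clears in minutes. Both features hide what happened at home.

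The treatment under test is a week of twice-daily use, or 14 administrations per condition. In the first week the protocol describes the first dose and the two laboratory doses as taken on site. If those count within the 14 (an assumption), 14 - 3 = 11 are unobserved. Without a usable measure of them, a null result cannot be separated from non-use at home. A positive result cannot be credited to the week of dosing rather than to the dose taken shortly before the cue task.

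**Working it through.** **Inputs.** Half-life 3-17 min, in serum (section 7, Oxytocin). Laboratory dose to first saliva oxytocin sample: 30 min (section 3, Visit 3). Home use: twice a day (section 3).

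**Assumptions.** Elimination is first-order. Saliva clears broadly like serum. Home and laboratory doses are equal. The documents do not give the gap between the last home dose and the sample, so 1 to 12 h is shown.

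**Formula.** Fraction of a dose left after t minutes = 2^(-t/half-life).

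| Time from dose to sample | Half-life 17 min | Half-life 3 min |
|---|---|---|
| 30 min (laboratory dose) | 2^(-30/17) = 0.294 | 2^(-30/3) = 0.00098 |
| 1 h | 0.087 | 9.5e-7 |
| 2 h | 0.0075 | 9.1e-13 |
| 4 h | 5.6e-5 | 8.3e-25 |
| 8 h | 3.2e-9 | 6.8e-49 |
| 12 h | 1.8e-13 | 5.7e-73 |

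**Home signal relative to laboratory signal at the sample.** This is 2^(-(t-30)/half-life). At 17 min it is 29% for a home dose 1 h before the sample, 2.5% at 2 h and 0.02% at 4 h. At 3 min it is 0.1% at 1 h and about 1e-9 at 2 h. If the home dose were half the laboratory dose, each ratio would halve (1.3% at 2 h with the 17-min half-life).

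**If the sample were taken before the laboratory dose.** At 17 min, a home dose falls below 5% after 17 x log2(20) = 73 min and below 1% after 17 x log2(100) = 113 min. Such a sample could show use in the last one to two hours, not over several days.

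**If saliva cleared more slowly.** For any half-life, 2^(-(t-30)/half-life) is below 1 once t exceeds 30 min. An equal dose taken in the laboratory therefore always outweighs any single earlier home dose in the sample.

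**Placebo week.** The placebo contains no oxytocin, so the level is the same whether or not the spray was used.

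**The case against.** The strongest reply is that adherence is covered elsewhere. Accountability is scheduled at all four laboratory visits, the bottle is returned, and the protocol lists attachments on drug use and medication management that are not in the material supplied. This stands as a limit on the point. A reader might infer that the protocol has no other check on home use, and the documents do not support that. They show that the compliance paragraph relies on levels without referring to accountability, and that the text supplied gives no method for it.

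A second reply is that the compliance paragraph does not name the sample. A blood vial for hormones is drawn before the laboratory dose, and the table mentions both blood and saliva. However, oxytocin is named only for saliva, and a pre-dose sample would still be limited to the last one to two hours on the serum half-life.

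Third, that half-life is for serum. This is correct, so the very small fractions depend on a stated assumption. The order of dosing and sampling does not.

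Two stronger readings are tempting. One is that the measure would show adherence even if no home dose were taken. At a 3-min half-life only 0.1% of the laboratory dose remains at sampling, so even that dose might not register, and in the placebo week nothing would. The other is that the levels would be used to rule out non-use after a null result. Neither document says so, and the SAP's intention-to-treat analysis does not condition on adherence. A spray dose also precedes the cue task at each laboratory visit, so exposure at the craving assessment does not depend on home use alone.

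**Conclusion.** The point holds in this form: the stated compliance measure is uninformative about home dosing, and it cannot do the job that the protocol gives it. With the longest stated half-life, a home dose leaves 0.75% at 2 h and about 3e-9 at 8 h, against 29% of the laboratory dose at sampling. With the shortest, 0.1% of the laboratory dose remains and the home signal is smaller still.

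These figures assume first-order elimination, equal doses and salivary clearance broadly like serum. The findings that the sample follows a laboratory dose and that placebo-week levels carry no information need none of these. The consequence is for interpreting a comparison of seven-day administration, not for the validity of the randomisation. Whether a sound accountability method already exists in the attachments cannot be judged from the text supplied.

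**What to change.** - In the Medication compliance paragraph, describe laboratory oxytocin levels as a measure of acute exposure.
- Base home adherence on the accountability item at Visits 3-6, and define it by bottle weight or remaining volume. Neither is specified in the text supplied, so the method has to be written in or cross-referenced to the attachments.
- Check the bottle for each condition at that condition's last laboratory visit (Visits 4 and 6), instead of a single return at the end.
- Report adherence descriptively by condition. Label any analysis by adherence as exploratory: it selects after randomisation, and the SAP's missing-data section counts only 16 within-subject and 4 between-subject participants.
- Reconcile the dose statements first, because expected bottle use depends on them. The section 3 Oxytocin paragraph gives 0.1 mL per spray, 2 sprays per nostril twice a day, and 40 IU as the daily total: 8 sprays x 0.1 mL x 7 days = 5.6 mL. Section 2, section 3 (Drugs and Doses) and section 5 give 40 IU twice a day, and Visit 3 equates 40 IU with 4 sprays per nostril: 16 sprays x 0.1 mL x 7 days = 11.2 mL, more than the 10-mL spray described.

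Before or during data collection, the cost is protocol wording and a short bottle check at existing visits. The SAP describes the trial in the past tense, as run in 2019-2023. If collection has ended, report whatever accountability data exist and do not present oxytocin levels as evidence of home compliance.

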Assessments: The CADRE CLC will provide a core assessment battery to all RPs to measure mechanisms underlying chronic disease. As described in the CLC Research Plan, these include measures of pain, trauma, family history of AUD/SUD, affect, behavioral dysregulation, physical activity, health-related quality of life. Biomarkers collected in all projects include: sleep, enzymes aminotransferase and alanine aminotransferase (AST, ALT), markers damage; creatinine and blood urea nitrogen, markers of kidney function; salivary cortisol, a marker of stress response; soluble CD14 (sCD14), a marker of monocyte activation; tumor necrosis factor alpha (TNF-α) and interleukin-6 (IL-6), pro-inflammatory cytokines; kynurenine/tryptophan ratio (Kyn/Tryp), implicated in neuropsychiatric symptoms associated with immune activation; and monocyte chemoattractant protein 1 (MCP-1), a chemokine that regulates migration and infiltration of monocytes/macrophages and is involved in various neuroinflammatory disorders.

THE BLUE TEXT IN THE FOLLOWING SECTIONS IS A GUIDE TO ENSURE ALL RELEVANT INFORMATION IS INCLUDED IN YOUR APPLICATION. YOU MAY DELETE THE BLUE TEXT BEFORE SUBMISSION

4. Participant Population.

One hundred individuals receiving buprenorphine/naloxone as opioid replacement therapy (ORT) will be screened randomized. We included individual receiving ORT because we specifically target risk of relapse in a treatment-seeking population. No vulnerable population will be included in the study.

INCLUSION CRITERIA

- ~Male or female (50%), 18 to 70 (inclusive) years of age;
- Currently meets DSM-5 criteria for OUD;
- Currently on a stable dose of buprenorphine/naloxone or methadone for at least 3 months:
- In good health as confirmed by medical history, physical examination and blood work (AST/ALT; bilirubin, creatinine clearance within normal limit);
- Willing to take medication and adhere to the study procedures;

- Understand informed consent and questionnaires in English at an 8th grade level;
- Clinical Opiate Withdrawal Scale (COWS) = 0 at study screening and prior laboratory sessions.

> EXCLUSION CRITERIA

- Women who are breastfeeding, test positive for pregnancy or are unwilling to use medically-approved birth control;
- Liver function within 5x the Upper normal limits (AST/ALT) and renal function within 2x the Lower Normal Limit (bilirubin, creatine clearance).
- Suicide attempts in the last three months;

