Outcomes: Primary (craving) and secondary (safety and tolerability) outcomes were assessed in realtime in the laboratory. Seven-day oxytocin administration was compared to the oxytocin-matched placebo condition during the CR procedure, in which noradrenergic activation produced by yohimbine or yohimbinematched placebo condition (2X2 design) was measured. We used Generalized Linear Model (GLM) with modelbased estimator in the covariance matrix, with medication (oxytocin/placebo) and noradrenergic activation (yohimbine/placebo) as within-subject factors. The model was specified to evaluate the effect of drug (oxytocin/placebo) by noradrenergic (vohimbine/placebo) interaction, main effect of the drug, and main effect of noradrenergic activation. Craving was assessed using the DDQ with time coded as: t_0 =relaxation, t_1 =interaction with drug paraphernalia/opioid auditory cues and t_2 =opioid use video. Safety and tolerability were assessed using: SBP, DBP, HR (vital signs), HAM-A and STAI (anxiety). The STAI y1 (state) was included as an additional safety measure for anxiety to ensure participants were not experiencing acute symptoms of anxiety within the laboratory. The STAI y2 (trait) was inserted as a covariate in the model to control for baseline anxiety level, along with stress (PSS), HPA (cortisol), and noradrenergic response (α -amylase). Time at laboratory sessions was coded as: t_0 =baseline, t_{45min} =45-min after yohimbine administration, and t_{90min} =post cue-exposure to specifically evaluate the contribution of each laboratory procedure (vohimbine and CR). Withdrawal symptoms (COWS) and AEs were assessed at specific timepoints: t_0 =pre-laboratory and t_1 =post-laboratory procedures.

Other outcomes (safety and tolerability) were measured retrospectively during the one-week outpatient setting and included the: COWS (withdrawal), anxiety (HAM-A and STAI), stress (PSS), depression (HAM-D) and AEs. The other outcomes were analyzed using ANOVA test and the number of AEs via a χ^2 test. For missing data approach, we first categorized missing data as missing completely at random (MCAR), missing at random (MAR) or missing not at random (MNAR)⁷. Analysis with GLM (using all available pairs of data to model missing values with maximum likelihood estimation) was deemed suitable for our analyses because no systematic differences existed between participants with missing data and those with complete data (MCAR)⁸.

Missing data reporting ⁹

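### If COWS = 0 is enforced before each laboratory session, the pre-session COWS (t0), and apparently the outpatient-week COWS, cannot show a withdrawal difference between sprays

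*Protocol*

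**What the plan says.** **Protocol, Part III section 4 (Inclusion criteria):** "Clinical Opiate Withdrawal Scale (COWS) = 0 at study screening and prior laboratory sessions". I read this as before each laboratory session.

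**Protocol, Part III section 7 (protections against risk, item 6):** "Opioid withdrawal will be assessed before each visit", with the expectation of mild withdrawal justified because "individuals with a COW > 0 will be excluded from the study at screening". No consequence is given for a positive score at a later visit.

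**Protocol, Part III section 3 and Table 1:** COWS is listed at every visit. Visit 2 is randomisation and first dose. Visits 3 to 6 are the laboratory sessions, the first on Day 5. The Visit 3 description places the Table 1 assessments before the yohimbine or matching-placebo capsule.

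**SAP, Statistical analysis, Outcomes:** COWS appears twice. In the laboratory, "Withdrawal symptoms (COWS) and AEs were assessed at specific timepoints", namely "t_0 =pre-laboratory and t_1 =post-laboratory procedures". For the spray week, "Other outcomes (safety and tolerability) were measured retrospectively during the one-week outpatient setting and included the: COWS (withdrawal" and further scales. On the test for this second group: "The other outcomes were analyzed using ANOVA test".

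**The concern.** A rating that decides whether a session goes ahead is also one of the safety outcomes read from that session. A participant who develops withdrawal during a spray week would not contribute a positive t0 score. That participant would appear, if at all, as a session not held or held later.

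The protocol lists withdrawal among the participant risks, and Aim 3 concerns tolerability in people on opioid replacement therapy. The spray-week COWS is the measure meant to reflect a week of home dosing, as distinct from the acute effects of the laboratory procedures. If it comes from the same pre-session rating, a finding of no difference in withdrawal would be produced by the entry rule and would say nothing about the spray.

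**Working it through.** The plan gives no figure to reproduce on this point. The check is a comparison of the texts, then simple arithmetic.

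**1. Is any COWS rating taken on spray free of the criterion?** From Table 1 and the visit descriptions:
- Visit 1: before any spray.
- Visit 2: randomisation and first dose, so no exposure period yet.
- Visits 3 to 6: after several days of spray, and subject to the criterion.
- Visit 7: three days after the last session, so it bears on the second spray only.
- Visits A and B: for re-enrolled participants only. A is a renewed eligibility check and B follows Visits 5 and 6.

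No unconstrained rating is scheduled during a spray week. The only unconstrained laboratory rating is the SAP's t1, taken after the procedures.

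**2. What does enforcement do to t0?** Let p₁ and p₀ be the true probabilities of COWS > 0 at a scheduled session on oxytocin and on placebo. Among sessions held, P(COWS > 0 | held) = 0 on both sprays, so the observed difference is 0 − 0 = 0 whatever p₁ − p₀ is. Running the ANOVA and a paired t-test on all-zero scores at n = 16 (the SAP's within-subject count) and at n = 50 (the protocol's planned completers) gives variance 0 and undefined F, t and p. A larger sample does not help.

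**3. Where would the information go?** Into sessions that fail the check. With 16 participants and two sessions per spray, the expected number is 2 × 16 × p = 32p per spray. The documents give no value for p. Over an assumed range of 0.05 to 0.30, this is 32 × 0.05 = 1.6 to 32 × 0.30 = 9.6 sessions. Neither document plans to report this count.

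**4. What would a genuine absence of withdrawal show?** If all 16 participants truly scored 0 at a given visit, the one-sided 95% upper bound on the probability of a positive score is 1 − 0.05^(1/16) = 0.171. That is informative but wide, and it can be claimed only if nobody was removed or deferred.

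**5. What can t1 carry?** It is free to vary. The paired standardised difference detectable with 80% power at two-sided 0.05 (normal approximation) is (1.960 + 0.842)/√n:
- n = 16: 2.802/4 = 0.70
- n = 50: 2.802/7.071 = 0.40

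**6. Do the documents agree on the rule?** The inclusion list extends the criterion to the sessions. The risk section attaches exclusion to screening and otherwise speaks only of assessment. Neither says that a session is cancelled, postponed or run regardless, or what becomes of the score.

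**The case against.** **The SAP reports no loss due to COWS.** Its missing-data section gives only the design change and cardiovascular safety concerns as reasons. One may argue that either the check never failed, in which case 0 versus 0 is a true observation, or it was not applied, in which case nothing was truncated. Both cases are possible. But that section accounts for participants who missed a whole spray or yohimbine condition. A single session withheld or moved to another day would leave no trace there, so a third case remains open.

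**The source of the outpatient-week COWS is inferred.** This stands. The SAP does not name the rating, and Table 1 does not account for the SAP's whole outpatient list: the PSS is absent from it, and the HAM-D is scheduled only at Visits 1 and A. Another source is possible, and the claim about this outcome is worded accordingly.

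**Aim 3 does not rest on t0.** This also stands. A reader might infer that the tolerability aim as a whole is uninformative. The documents do not support that, because t1 COWS, adverse events, blood pressure, heart rate, HAM-A and STAI are untouched by the criterion.

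**Craving.** A reader might also infer that the craving comparison is biased by selecting weeks free of withdrawal. Enforcement could have that effect, and such losses would not fit the SAP's missing-completely-at-random justification. But neither document says that a session was withheld, and neither gives a rate or a link between withdrawal and craving. The effect is possible and cannot be quantified.

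**Conclusion.** The point holds in a limited form. If the inclusion criterion is applied before each session, the t0 COWS comparison between sprays is 0 versus 0 by construction. The same appears true of the outpatient-week COWS. Neither could then support a statement that oxytocin does or does not affect withdrawal.

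This rests on two assumptions: that the criterion was enforced at sessions, which the risk section leaves in doubt, and, for the outpatient-week score, that it is the pre-session rating. The documents do not show that any session was lost, that Aim 3 fails, or that the craving result is distorted.

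The matter should be settled before any withdrawal result is reported, but it does not undermine the trial as a whole.

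**What to change.** 1. Reconcile the inclusion criterion, the risk section and the SAP on whether COWS = 0 applies at each session, and state what happens to the session and its data otherwise. I take no view on which rule is right.
2. State in the SAP which COWS rating enters each comparison, and in particular the source of the outpatient-week score.
3. Keep the COWS taken at each scheduled Visit 3 to 6 before the criterion is applied. The SAP describes a completed trial with a locked database, so in practice this means recovering the scores from visit records.
4. Analyse any COWS above 0 at the scheduled visit by spray condition, including sessions withheld or rescheduled for it, and report the number of such sessions by spray.
5. If those scores were not kept, state that the t0 and outpatient-week COWS comparisons are uninformative and make no claim of no withdrawal effect from them. Rest the withdrawal result on t1, noting that it follows the yohimbine or matching-placebo dose, a laboratory spray dose and the cues, in people selected to start at 0.

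The cost is wording in both documents, a record check and one extra table. No new assessment is needed, because COWS is already scheduled at these visits.
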